12	INTERIM ANALYSIS	33
13	CHANGES IN PLANNED ANALYSIS.....	33

LIST OF ABBREVIATIONS

AATD	Alpha ₁ -antitrypsin deficiency
ADR	Adverse drug reaction
AE	Adverse event
Alpha-1 MP	Alpha ₁ -proteinase inhibitor (human), modified process
Alpha ₁ -PI	Alpha ₁ -proteinase inhibitor
ALT	Alanine aminotransferase
AST	Aspartate transaminase
ATS	American Thoracic Society
AUC	Area under the concentration-time curve
BLQ	Below limit of quantification
C _{max}	Maximum concentration
COPD	Chronic obstructive pulmonary disease
CRF	Case report form
CV	Coefficient of variation
FEV ₁	Forced expiratory volume in 1 second
FVC	Forced vital capacity
GCP	Good Clinical Practice
HAV	Hepatitis A virus
HBV	Hepatitis B virus
HCV	Hepatitis C virus
HIV	Human immunodeficiency virus
IgA	Immunoglobulin A
IgG	Immunoglobulin G
IgM	Immunoglobulin M
MedDRA [®]	Medical Dictionary for Regulatory Activities
NE	Neutrophil elastase
PFT	Pulmonary Function Test
PI*MM	Proteinase inhibitor homozygote for normal M allele
PI*(null)(null)	Proteinase inhibitor homozygote for (null) allele
PI*SZ	Proteinase inhibitor heterozygote for S and Z deficiency alleles

PI*Z	Proteinase inhibitor Z deficiency allele
PI*ZZ	Proteinase inhibitor homozygote for Z deficiency allele
pH	Potential of hydrogen; acidity/alkalinity measure
PK	Pharmacokinetics
SAE	Serious adverse event
SAP	Statistical analysis plan
SD	Standard deviation
t ^{1/2}	Terminal half-life
TEAE	Treatment-emergent adverse event
t _{max}	Time to reach C _{max}
US	United States
WHO-DD	World health organization drug dictionary

1 Purpose of the Analysis

The purpose of this statistical analysis plan (SAP) is to outline the planned analyses to support the completion of the clinical study report (CSR) for protocol GTI1401 and GTI1401-OLE. The planned analyses identified in this SAP will be included in regulatory submissions and/or future manuscripts. Exploratory analyses not identified or defined in this SAP may be performed to support the clinical development program. Any post hoc or unplanned analyses performed and not identified in this SAP will be documented in the respective CSR.

2 Introduction

Alpha₁-antitrypsin deficiency (AATD) is a genetic disorder in which mutations of the SERPINA1 gene (a member of the SERPIN, serine protease inhibitor gene family) lead to a reduced serum level of the serine protease inhibitor called alpha₁-proteinase inhibitor (alpha₁-PI) or, historically, alpha₁-antitrypsin. AATD manifests clinically as pulmonary emphysema, chronic obstructive pulmonary disease (COPD), and liver cirrhosis.

The most frequent mutation causing severe AATD is called PI*Z and was first described in a Swedish patient with emphysema. PI*MM (normal) individuals have serum alpha₁-PI levels in the range of 20 to 53 μ M; however, PI*ZZ (homozygous abnormal) individuals with AATD have serum alpha₁-PI levels in the range of 2 to 10.2 μ M. The estimated world-wide prevalence of PI*ZZ and PI*SZ (heterozygous abnormal) individuals is approximately 163,700 and 903,000, respectively.

Like other hereditary disorders, AATD is relatively rare (e.g., has orphan drug designation); however, it is extremely rare among Asians. In 2000, a survey supported by the Japanese Ministry of Health and Welfare identified only 16 individuals in Japan with documented AATD. AATD in Japanese patients exhibits unique features compared to AATD in Caucasians, including the lack of a PI*Z variant and a high incidence of the S_{iiyama} deficiency AATD variant. In Japanese patients homozygous for the S_{iiyama} variant, serum alpha₁-PI levels are in the range of 2.1 to 7.7 μ M. Japanese normal individuals have serum alpha₁-PI levels in the range of 21 to 34 μ M (94 to 150 mg/dL as measured by nephelometry, which is used as the laboratory test standard values).

Augmentation therapy with intravenous (IV) alpha₁-PI is administered in patients with AATD to increase the low serum concentrations in this patient population. This usage is intended to bolster the protective protease inhibitory shield against increased numbers of lung neutrophils releasing increased concentrations of NE, leading to a corrected protease: antiprotease imbalance. The restored antiprotease shield then protects the lung from elastolytic damage and slows the development of pulmonary emphysema.

Alpha₁-PI (human), Prolastin[®], was licensed for use as augmentation therapy for AATD, at a dose of 60 mg/kg weekly, in the United States (US) in 1987 and in Germany in 1988. To date, Prolastin[®] has been approved in 20 countries including the United States and European countries. Subsequently, Grifols incorporated modifications into the Prolastin manufacturing process to produce alpha₁-PI (human), modified process (Alpha-1 MP).

This modified process results in an increased yield of alpha₁-PI and a product with twice the alpha₁-PI concentration with an improved pathogen safety profile and higher purity compared to Prolastin. Alpha-1 MP is approved for 60 mg/kg weekly IV administration in the US, Canada, Argentina, Columbia, Turkey, Chile and Australia for the treatment of patients with severe AATD and clinically evident emphysema under the trade name Prolastin[®]-C.

Japanese patients with AATD exhibit very different genotypes of AATD compared to the rest of the world, and the number of Japanese patients with AATD is extremely small. These subjects can exhibit symptoms of emphysema-typed COPD and therefore, will have clinically evident emphysema and along with alpha₁-PI deficiency. The safety and PK of augmentation therapy with Alpha-1 MP to increase serum alpha₁-PI levels has not been evaluated in Japanese patients with AATD. Thus, Grifols Therapeutics LLC and Grifols Japan K.K. is conducting a study to assess the safety and PK of 60 mg/kg Alpha-1 MP administered by weekly IV infusions over 8 weeks in Japanese subjects with AATD.

3 Objectives

3.1 Primary Objectives

The primary objective of GTI1401 study is to evaluate the safety of 60 mg/kg Alpha-1 MP administered by weekly IV infusions over eight weeks in Japanese subjects with AATD.

The primary objective of GTI1401-OLE study is to evaluate the long-term safety of 60 mg/kg Alpha-1 MP administered by weekly IV infusions for approximately one year or longer (can be renewed annually with the consent of the subjects) in adult subjects with AATD in Japan.

3.2 Secondary Objectives

The secondary objective of GTI1401 study is to evaluate the trough level of total alpha₁-PI for weekly IV infusions of 60 mg/kg Alpha-1 MP in Japanese subjects with AATD.

The secondary objective of GTI1401-OLE study is not set up.

3.3 Exploratory Objectives

The exploratory objective of GTI1401 is to measure the following PK parameters for Alpha₁-PI at steady state at the end of the 8-week treatment period.

- AUC_{0-7 days}
Area under the concentration-time curve (AUC) from Day 0 to Day 7, calculated at steady state at the end of the 8-week treatment period.
- C_{max}
Maximum concentration
- t_{max}
The observed time to reach C_{max}
- t_{1/2}
Terminal half-life

The exploratory objective of GTI1401-OLE is to perform CT scan (densitometry) annually starting at Ext Week 52. The CT scan data will be accumulated for the future evaluation of lung density.

- CT scan (densitometry)
Note: Subjects will undergo CT scanning for diagnosis of clinically apparent pulmonary emphysema in GTI1401 study. This CT scan data will also serve as the baseline measurement of lung density for GTI1401-OLE study.

4 Investigational Plan

4.1 Study Design and Plan

GTI1401 study is a multi-center, open-label, trial to evaluate the safety and PK of weekly IV infusions of 60 mg/kg Alpha-1 MP in Japanese subjects with AATD. At least three adult subjects will be enrolled in the study. The study consists of an up to three-week Screening Period, and an eight-week open-label Treatment Period including a one-week PK Assessment Period after the last infusion. At the Week 9 visit when the PK evaluation period is completed, subjects will be asked whether they would like to participate in an extension trial (GTI1401-OLE). For subjects not intending to participate in the extension trial, the date of follow-up/study completion visit (30 days [4 weeks] after the last dose of the investigational drug) will be arranged. The total duration of study participation for subjects who complete the study will be up to 14 weeks.

After providing informed consent at the Screening Visit, subjects will be evaluated for study eligibility during the Screening Period (up to three weeks); for study inclusion and exclusion criteria. Eligible subjects will enter the eight-week Treatment Period to receive

a total of eight weekly IV infusions of 60 mg/kg Alpha-1 MP; subjects will receive their first infusion of Alpha-1 MP at the Week 1 (Baseline) Visit. During the Treatment Period, weekly infusions of Alpha-1 MP will be performed at the study site during scheduled study visits at Weeks 1 (Baseline), 2, 3, 4, 5, 6, 7, and 8. Subjects will receive their last infusion of Alpha-1 MP at the Week 8 Visit and will then enter the one-week PK Assessment Period. During the PK Assessment Period, subjects have a last PK blood sampling study visit at Week 9. A Follow-Up/Final Visit (30 days [4 weeks] post last study drug infusion) will occur for subjects who will not participate in Study GTI1401-OLE.

[figure not shown]
All subjects will have a blood sample collected at Weeks 1 (Baseline), 7, and 8 (prior to the infusion of Alpha-1 MP) and Week 9 which will be used for the measurement of trough alpha₁-PI levels.

Blood samples for PK parameters will be collected beginning at Week 8 and the collection of blood samples will extend into Week 9. The pre-infusion serial PK sample at Week 8 and the last serial PK sample (7 days after the Week 8 infusion) at Week 9 will also serve as trough blood samples for Weeks 8 and 9. The specific timing of all 10 serial blood samples includes:

- Immediately prior to infusion
- Immediately after infusion completion (after sodium chloride [NaCl] flush) (0 hour)
- 15 minutes after infusion completion
- 2 hours after infusion completion
- 4 hours after infusion completion
- 8 hours after infusion completion
- 24±4 hours (1 day after infusion completion)
- 48±4 hours (2 days after infusion completion)
- 120 hours ± 1 day (5 days after infusion completion)
- 168 hours ± 1 day (7 days after infusion completion) (Week 9 Visit)

At the Week 9 visit, subjects have the option to participate in an open-label extension (OLE) study (GTI1401-OLE) in which subjects, if they opt to enroll, will continue to receive 60 mg/kg Alpha-1 MP for at least another year (with the optional subsequent annual extensions) to assess the long-term safety of Alpha-1 MP. Week 9 of the GTI1401 study is also the first week of the extension study (GTI1401-OLE). If subjects do not opt to participate in Study GTI1401-OLE, they will come back to the clinic 30 days (4 weeks) after the last Alpha-1 MP infusion for the Follow-Up/End of Study Visit (Week 12).

A schematic of the overall study design is shown in Figure 1 below. The schedule of events for GTI1401 and GTI1401-OLE studies can be found in appendix 1 and appendix 2.

- Final Visit/Early Termination = Follow-up/Final Evaluation Visit. Subjects who discontinue early from the study will need to complete this study visit 30days (≈ Weeks) after the last study drug infusion.
- At the Week 9 visit, subjects will be given the option to participate in the GTI1401-OLE. If they are enrolled in Study GTI1401-OLE, the Week 9 visit will be their End of Study Visit of GTI1401 study.

Figure 1 Overall Study Schema

4.2 Study Variables

No efficacy variables will be assessed for the studies. The variables to be assessed for GTI1401 and GTI1401-OLE studies are as follows:

- Adverse events, ADRs, serious AEs (SAEs), and discontinuations due to AEs or SAEs
- Vital signs (heart rate, blood pressure, respiratory rate, and temperature)
- COPD exacerbations
- Pulmonary function tests :
 - Forced Expiratory Volume in 1 second (FEV₁)
 - Forced Vital Capacity (FVC)
- Clinical laboratory parameters:
 - Chemistry
 - Hematology
 - Urinalysis
- Alpha₁-PI trough level
- PK parameters (GTI1401 study only):
 - AUC_{0-7 days}
 - C_{max}
 - t_{max}
 - t_{1/2}
- CT scan (densitometry)

5 General Statistical Considerations

All analyses will be conducted using SAS Version 9.3 or higher.

Pharmacokinetic evaluations, descriptive statistical analysis of concentrations and PK parameters according to non-compartmental standard methods, as well as graphical representation of concentrations will be performed using the computer program Pharsight Phoenix WinNonlin (Version 6.1 or higher).

Unless otherwise specified, the results from GTI1401 and GTI1401-OLE will be presented separately.

Unless otherwise noted, for continuous variables, descriptive statistics will include the number of non-missing values, mean, standard deviation, median, minimum and maximum. For categorical variables, descriptive statistics will include counts and percentages per category.

5.1 PK Data Handling

For PK parameter estimation, the actual sample time instead of nominal time will be used. For the last time point (168 hours post infusion), if the actual time deviates from the scheduled time, the interpolation or extrapolation will be used to obtain the $AUC_{0-7\text{days}}$.

When BLQ values are recorded, adopt the half value of the readable numeric value (2.5 mg/dL) for summarizing data.

5.2 Handling of Missing values

Missing values will not be imputed unless otherwise specified.

For Adverse Event

Any missing severity/relationship will be accounted as “worst case” as related in the tables.

5.3 Safety Data Handling

5.3.1 Definition of Baseline

Baseline evaluations will be those collected (non-missing) closest to and prior to the first study drug infusion, which will be conducted –within 21 days of Week 1. For both GTI1401 and GTI1401-OLE, the baseline is the baseline visit at Week 1 in GTI1401 study.

For Pulmonary Function Tests

Values collected at “PRE-BRONCHODILATOR” time-point in screening visit will be defined as baseline for “PRE-BRONCHODILATOR”. Also values collected at “POST-BRONCHODILATOR” time-point in screening visit will be defined as baseline for “POST-BRONCHODILATOR”.

5.3.2 Visit Windows for Safety Analyses

The date of all visits after the screening visit and the Week 1 (baseline) visit will be arranged within a time window of ± 1 day.

If an observation is missing at a specific scheduled visit, the value at that visit will be set to missing.

Visit recorded on CRF will be used as Analysis visit except Baseline visit.

5.3.3 Unscheduled Visit

Data collected as unscheduled visits will not be used for the tables but presented in the listing and subject data plot.

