11.2.2 Summary Shift Table of Laboratory Test (Low, Normal and High)	
11.2.3 Summary Shift Table of Laboratory Test (Normal and Abnormal)	
Population	: Safety population
Contents	: Shift tables for laboratory test with normal range will be provided. The analysis variables are defined in appendix for laboratory parameter.
Analysis Visit for 1401	: Baseline, Week 5 , Week 9
Analysis Visit for 1401- OLE	: Baseline, and all scheduled visits (Bi-Annual Visits) starting from Ext Week 26.

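### Laboratory shift tables use scheduled visits only and have no worst post-baseline row, so an abnormality found only at an unscheduled visit never enters a laboratory table

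*SAP*

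**What the plan says.** Section 5.3.3 sets one rule for all unscheduled data: "Data collected as unscheduled visits will not be used for the tables but presented in the listing and subject data plot". It names no exception.

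Sections 11.2.2 and 11.2.3 plan two shift tables, one by low, normal and high and one by normal and abnormal: "Shift tables for laboratory test with normal range will be provided". The visits are "Baseline, Week 5 , Week 9" for GTI1401 and "Baseline, and all scheduled visits (Bi-Annual Visits) starting from Ext Week 26" for the OLE. The summary table in 11.2.1 uses the same visits.

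Section 5.3.2 governs how a result is assigned to a visit: "Visit recorded on CRF will be used as Analysis visit except Baseline visit". For gaps it says: "If an observation is missing at a specific scheduled visit, the value at that visit will be set to missing".

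Section 3.1 makes safety the primary objective: "The primary objective of GTI1401 study is to evaluate the safety of 60 mg/kg Alpha-1 MP administered by weekly IV infusions over eight weeks". The OLE has long-term safety as its primary objective.

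**The concern.** Of the planned tables, only the shift tables show movement between normal and abnormal laboratory values against a reference range. They give a check that does not depend on whether the investigator judged a value to be an adverse event. If a value outside the range is seen only between scheduled visits, that check does not register it. The subject can be tabulated as normal at baseline and normal at every later visit while the listing in the same report shows an abnormal result.

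Section 1 says that these analyses support the study report and will be included in submissions or manuscripts. A reader who sees the summary tables without the listing would not learn of the value.

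**Working it through.** The SAP states no figure on this point, so there is none to reproduce. The check is whether an unscheduled laboratory result has any route into a laboratory table.

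**Routes**

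1. *Directly, as an unscheduled visit.* Closed by 5.3.3.
2. *By reassignment to a nearby scheduled visit.* Closed by 5.3.2: after baseline, the visit label on the CRF is the analysis visit.
3. *As a replacement for a missing scheduled value.* Closed by 5.3.2: the scheduled value stays missing.
4. *Through a worst-value, any-time or treatment-emergent laboratory summary.* None is planned in 11.2.1 to 11.2.3.
5. *Through the adverse event tables.* Open, but conditional. The adverse event definition in section 11 covers abnormal laboratory findings, and tables 11.1.1 to 11.1.6 are not by visit. The value is counted only if it is reported as an event.
6. *Listing and plot.* Open. Section 11.2.1 commits to a laboratory listing. Section 5.3.3 also names a subject data plot, but the figures specified in the text at hand are for alpha₁-PI concentration (10.1.3, 10.1.4) and lung density (10.2.2, 10.2.3), not for laboratory data.

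So a value that is unscheduled and not reported as an adverse event reaches the listing, and possibly a plot, but no table.

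**Spacing of tabulated values**

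- GTI1401: Week 1 to 5 and Week 5 to 9, each 4 × 7 = 28 days.
- OLE: Ext Week 1 to 26, 25 × 7 = 175 days; Ext Week 26 to 52, 26 × 7 = 182 days.

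If an abnormality lasts D days and starts uniformly within a gap of G days, the chance that it is still present at the next scheduled visit is min(1, D/G). The durations D are assumptions.

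| D (assumed) | G = 28 | G = 175 | G = 182 |
|---|---|---|---|
| 7 days | 25% | 4.0% | 3.8% |
| 14 days | 50% | 8.0% | 7.7% |
| 28 days | 100% | 16.0% | 15.4% |

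These figures describe how sparse scheduled sampling is. They do not measure what 5.3.3 removes, which depends on how many unscheduled tests are done and what they show. The SAP does not give that.

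**Effect on a cell**

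Section 5.4 targets at least 3 subjects. One omitted case is 0/3 = 0.0% against 1/3 = 33.3%. Any single event among three subjects gives this change, so it is only an illustration.

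**Baseline**

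Section 5.3.1 selects by proximity: "Baseline evaluations will be those collected (non-missing) closest to and prior to the first study drug infusion". It also names the Week 1 visit as baseline, and 5.3.2 exempts baseline from the CRF label. Appendix 1 schedules laboratory sampling at Screening and again at Week 1, with note g placing the latter before the infusion. A repeat taken between the two is further from the first infusion than the Week 1 sample, so 5.3.1 would not select it. An unscheduled value competes for baseline only if the Week 1 sample is missing or a further pre-dose draw follows it. For pulmonary function, 5.3.1 fixes baseline at screening and the question does not arise.

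**The case against.** The strongest case for leaving the plan alone is that limiting by-visit tables to scheduled visits is usual practice, the rule is prespecified and clear, and the values remain visible. With about three subjects and descriptive statistics only, a listing can be read in full. An abnormal finding reported as an adverse event is counted by system organ class, severity and causality whenever it occurred. A worst-value row brings its own tilt, because more testing gives more chance of an abnormal result. All of this stands, and it limits the weight of the point. It does not supply the missing display: reporting as an adverse event rests on judgement, and the shift table would still disagree with its own listing.

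A reader might infer more than the SAP supports:

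- *That laboratory safety signals are kept out of every table, or hidden.* They are not. The gap concerns laboratory tables; the adverse event tables and the listing remain.
- *That the rule selectively removes abnormal values and biases the tables toward no finding.* The SAP does not say why unscheduled tests are ordered, and the rule applies equally to normal repeats.
- *That nothing beyond Weeks 5 and 9 can be tabulated in GTI1401.* Section 5.3.4 puts Week 12 data into the safety tables for subjects who do not enter the OLE, although 11.2.1 to 11.2.3 do not list that visit.
- *That 5.3.1 and 5.3.3 contradict each other outright.* They meet only in the narrow case set out under baseline.

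**Conclusion.** The point holds as a gap in presentation. By-visit shift tables, together with 5.3.2 and 5.3.3, leave no laboratory table for an abnormality found only at an unscheduled visit. If it is also not reported as an adverse event, it appears only in the listing and any plot, and the shift table can show the subject as normal throughout. This rests on the wording of the SAP alone.

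The consequence is modest. No data are lost, and no sample size, error rate or formal test changes. How often it would happen cannot be derived from the document. It is worth correcting because safety is the primary objective of both studies and the change costs almost nothing. The baseline question needs at most one clarifying sentence.

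**What to change.** - Keep all by-visit rows in 11.2.1 to 11.2.3 on scheduled visits.
- Add one row per parameter to 11.2.2 and 11.2.3: worst post-baseline value, scheduled or unscheduled. In 11.2.2, say how a subject with both a low and a high value is counted. For the OLE, say that only values after its own first infusion count, because its baseline is Week 1 of GTI1401.
- Except this row from 5.3.3.
- Footnote that subjects tested more often have more chance of an abnormal worst value.
- Add one sentence to 5.3.1 or 5.3.3: an unscheduled pre-dose value may serve as baseline when the scheduled Week 1 pre-infusion sample is missing.

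The cost is one row per parameter in two tables, two sentences and a footnote. No extra data collection is needed. The downside is the one that the footnote states.

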5.3.4 Follow-Up/End of Study Visit

30 days [4 weeks] after the completion of the last Alpha-1 MP infusion (Week 8) and 3 weeks after the Week 9 Visit, those subjects who do not participate in Study GTI1401-OLE will go to the clinic to complete a Follow-Up/End of Study Visit (Week 12). The Week 12 Visit should be scheduled at the protocol-specified study week relative to the date of the Week 1 (Baseline) Visit ± 1 day. The data collected during Follow-Up/End of Study Visit (Week 12) are included in Table and Listing for Safety Analysis and Concomitant Medication.

5.4 Sample Size

The targeted sample size is at least 3 subjects. Sample size was chosen based on clinical considerations and the number of available Japanese patients with AATD, not on a formal sample size calculation.

